# 8.8 Interim Analysis

An IA is planned to occur at approximately 67% information fraction, i.e., when data become available for approximately 217 participants from the ITT population, including those that discontinued earlier than 8 weeks. The interim data will not include any participants with partial data to keep the cohorts before and after the IA independent. This IA is intended to evaluate whether the data are sufficient to declare success for efficacy early, but not for evaluating futility. As such, the IA will use an efficacy boundary but will not have a futility boundary specified.

success is 0.007 on the p-value scale; that is if the p-value is smaller than 0.007 at this IA,

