#### STATISTICAL METHODS:

This trial is a randomized, double-blind, placebo-controlled, Phase 3 trial with an approximate sample size of 324 participants. An interim analysis (IA) is planned when 8-week data are available for approximately 217 participants (67% information fraction) in the intent-to-treat (ITT) population, including those that discontinued earlier than 8 weeks (e.g., due to lost-to-follow-up, withdrawal of consent). This IA is intended to evaluate whether the data are sufficient to declare success for efficacy early based on primary efficacy endpoint, but not for evaluating futility.

Determination of Sample Size

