### 1.4 Summary of Trial Design

This trial is composed of 2 parts: A) Part A is a randomized, double-blind, placebo-controlled trial and B) Part B is an *optional* open-label treatment (OLT) arm for participants who experience an on-trial central laboratory-positive *C. difficile*-related diarrhea through Week 8 (Figure 5).

- **Part A** will evaluate the efficacy, safety and tolerability of CP101 versus placebo for the prevention of recurrent CDI
- **Part B** is an *optional* OLT arm evaluating the efficacy, safety, and tolerability of CP101, in eligible participants from Part A who experience an on-trial central laboratory-positive *C. difficile*-related diarrhea through 8 weeks after receiving CP101 or placebo. See Part B, Section 6 of the protocol for further details regarding the OLT arm. Participants are not eligible to enter Part B of the trial without having been dosed in Part A first.

Participants with recurrent CDI who have received SOC CDI antibiotics (vancomycin, fidaxomicin, and/or metronidazole [Section 4]) will be randomized using an interactive response technology (IRT) system in a 2:1 ratio to CP101 or placebo. Participants should have completed a minimum of 10 days and a maximum of 21 days of SOC CDI antibiotics

Following randomization on Day 1, participants will

receive either CP101 or placebo.

Note: See Section 8.1 for definition of trial endpoints.

All participants will be followed through 8 weeks (Day  $57 \pm 3$  days) for the primary efficacy endpoint (hereafter referred to as Week 8) and to Week 24 (Day  $169 \pm 14$  days) for long-term safety endpoint (hereafter referred to as Week 24). The primary efficacy endpoint is the proportion of participants with CDI recurrence, through Week 8. CDI recurrence will be adjudicated by an independent blinded Adjudication Board (AB). For the primary safety endpoint, the incidence rate of treatment-emergent adverse events (TEAEs) will be presented by treatment group through Week 8. Participants will be followed through 24 weeks for other safety endpoints.

An interim analysis (IA) is planned after primary endpoint data is available for approximately 217 participants from the intent-to-treat (ITT) population (67% information fraction) (see Section 8.8). This IA is intended to evaluate whether the data are sufficient to declare success for efficacy early but not for evaluating futility.

A trial diagram outlining Part A and Part B and the trial visits is described in Figure 5.

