### 2.1 Primary Efficacy Objective, Endpoint, and Estimand

Primary Objective	Primary Endpoint
To evaluate the efficacy of a single oral dose of CP101 compared to placebo following SOC CDI antibiotics in preventing CDI recurrence in participants with recurrent CDI	Proportion of participants experiencing a CDI recurrence through Week 8 based on adjudication

The primary clinical question of interest is:

What is the difference in the proportions of participants experiencing CDI recurrence through 8 weeks after randomization to CP101 vs placebo in participants with recurrent CDI regardless of discontinuation of investigational intervention for any reason or change in background medication (dose and product)?

The estimand is described by the following attributes:

• Population:

Adult participants with recurrent CDI who have completed SOC CDI antibiotics for their qualifying episode

• Endpoint:

CDI recurrence through 8 weeks post randomization

• Treatment condition:

CP101 or placebo on Day 1 with 8 week follow-up for recurrence regardless of discontinuation of investigational intervention for any reason, or change in background medication (treatment policy strategy).

• Remaining intercurrent events:

The intercurrent events "intervention discontinuation for any reason" and "change in background medication (dose and product)" are addressed by the treatment condition of interest attribute.

The following intercurrent events will result in an outcome of "recurrence" for the primary efficacy analysis:

- Initiation of rescue medication for CDI (fecal microbiota transplantation [FMT] or full course of SOC antibiotics) prior to 8 weeks post randomization
- Occurrence of *C. difficile*-related diarrhea prior to 8 weeks in a participant who does not qualify for Part B of the study, per central lab testing algorithm, and discontinues the study for any reason
- Participants who enter into Part B of the study however, the *C. difficile*-related diarrhea episode is adjudicated as "no recurrence" by the AB
- Participants who die or experience another debilitating event prior to 8 weeks, which precludes continued participation in the study
- Participants who withdraw consent prior to 8 weeks after randomization
- Participants who are lost to follow-up prior to 8 weeks after randomization

There are no other intercurrent events anticipated at this time.

• Population-level summary:

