Participants will be followed through Week 8 after dosing for safety outcomes (all AEs and safety laboratory values), and primary efficacy outcomes. In addition, participants will be followed through Week 24 for long-term safety outcomes. AEs will be recorded from informed consent through Week 24 trial visit. Blood samples for safety laboratory analysis, will be collected at scheduled

trial visits per the Schedule of Assessments (Appendix 2; Table 3 [Part A] and Table 4 [Part B]).

The primary clinical outcome is CDI recurrence confirmed by an independent AB. Given that diarrhea is the key initial symptom of CDI recurrence, participants will be required to promptly report any new episode of diarrhea to trial site personnel (defined as > 3 unformed stools in 24 hours for 2 consecutive days). Participants who experience a new episode of diarrhea will undergo stool testing for *C. difficile* by central laboratory and an Investigator evaluation as outlined in Section 7.1.2 and Figure 8 [Investigator Assessment of a New Diarrhea Episode].

The maximum trial sample size is approximately 324 participants. An IA is planned when Week 8 data become available for approximately 217 participants from the ITT population (67% information fraction), including those that discontinued earlier than 8 weeks (e.g., due to a CDI recurrence, lost-to-follow-up, withdrawal of consent). This IA is intended to evaluate whether the data are sufficient to declare success for efficacy early but not for evaluating futility.

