# 6 PART B OPTIONAL OPEN-LABEL TREATMENT FOR RECURRENCE

#### 6.1 Summary

Part B (OLT) is the *optional* OLT arm of the trial and will similarly evaluate the efficacy, safety, and tolerability of CP101, in eligible participants from Part A. Participants in Part A, who experienced an on-trial central laboratory-positive *C. difficile*-related diarrhea within 8 weeks after receiving CP101 or placebo may be eligible.

Participants in Part A who experience a new episode of diarrhea within 8 weeks after Randomization (> 3 unformed stools in 24 hours for 2 consecutive days) will undergo central laboratory stool testing for *C. difficile*. The participant will have an Investigator evaluation (Figure 8) which will include a) review of diarrhea data; b) assessment of stool *C. difficile* testing by central laboratory testing algorithm (Figure 7); and c) the clinical decision to start a course of SOC CDI antibiotics. Participants with multistep central laboratory-positive *C. difficile*-related diarrhea will be eligible for Part B. All participants entering Part B will require confirmation of eligibility by the Medical Monitor.

Under extenuating circumstances and with approval of Medical Monitor, participants who experience *C. difficile*-related diarrhea in Part A may be allowed into Part B, provided there is positive multistep local laboratory *C. difficile*-related diarrhea AND the symptoms are clinically consistent with CDI recurrence.

Participants who meet eligibility criteria will be enrolled into Part B once eligibility has been confirmed. This participant cohort must have received SOC CDI antibiotics (vancomycin, fidaxomicin, and/or metronidazole [Section 4]) over a 10- to 21-day treatment period

All participants in the Part B cohort will be followed from the time of OLT administration of CP101 through their Week 8 trial visit (Day  $57 \pm 3$  days) for the assessment of the primary efficacy endpoint as well as safety follow-up and to Week 24 (Day  $169 \pm 14$  days) for other safety endpoints. Additional trial visits will occur as summarized in the Schedule of Assessments (Table 4). Blood and urine samples for safety laboratory analysis,

will be collected at scheduled trial visits per the Schedule

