#### of Assessments.

Part B will be independent of the participant's blinded trial group allocation in Part A (i.e., participants entering Part B may have received either CP101 or placebo in Part A). The participant-level blinding of initial trial group allocation will be maintained throughout the course of Part B for the participants, and Investigators. The Schedule of Assessment timelines will restart at Screening for participants who enter trial Part B. Visits are labeled by adding 'OLT-' in front of the visit number in the Schedule of Assessments (Table 4) to distinguish Part B trial visits from Part A trial visits. The secondary efficacy endpoint is the proportion of participants with CDI recurrence through Week 8 and Week 24 of Part B. For the secondary safety endpoint, the incidence rate of TEAEs will be presented by treatment group through Week 8 for Part B. Participants will be followed through 24 weeks for other safety endpoints. On-trial *C. difficile*-related diarrhea will undergo Investigator evaluation as outlined in Section 7.1.2.1. Surveillance for new episodes of diarrhea will be conducted as outlined in in Part A (Section 7.1.2.1) and in the Schedule of Assessments (Table 4).

The Investigator will check that all inclusion/exclusion criteria have been documented completely and the trial Medical Monitor will be required to confirm final eligibility for Part B. Screening for Part B (Section 6.2) may be combined with the relevant scheduled or unscheduled visit during Part A if feasible.

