# 8.10 Determination of Sample Size

The approximate sample size is 324 with an IA planned when 8-week data are available for approximately 217 participants from the ITT population (67% information fraction), including those that discontinued earlier than 8 weeks (e.g., due to lost-to-follow-up, withdrawal of consent). This IA is intended to evaluate whether the data are sufficient to declare "success" for efficacy early based on primary efficacy endpoint, but not for evaluating "futility." Further information on the definitions of success and futility will be included in the SAP.

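### Does the interim data cut let recent enrollees into the analysis only as failures?

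*Protocol*

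**What the plan says.** The trigger appears in five places in the protocol.

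- Synopsis, Statistical Methods: "An interim analysis (IA) is planned when 8-week data are available for approximately 217 participants (67% information fraction".
- Section 1.4: "An interim analysis (IA) is planned after primary endpoint data is available for approximately 217 participants".
- Section 3.1 asks for Week 8 data on about 217 ITT participants, "including those that discontinued earlier than 8 weeks (e.g., due to a CDI recurrence, lost-to-follow-up, withdrawal of consent".
- Section 8.10 has the same trigger, "including those that discontinued earlier than 8 weeks (e.g., due to lost-to-follow-up, withdrawal of consent"; recurrence is not among its examples.
- Section 8.8 also counts participants who left before 8 weeks, without examples, and then says: "The interim data will not include any participants with partial data to keep the cohorts before and after the IA independent". Success can be declared at p below 0.007. There is no futility bound.

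Two other sections bear on this. Section 2.1 lists the events scored as recurrence, among them rescue treatment for CDI, death, withdrawal of consent and "Participants who are lost to follow-up prior to 8 weeks after randomization". Section 6.1 says of those who recur and take open-label treatment: "The Schedule of Assessment timelines will restart at Screening for participants who enter trial Part B". That step follows antibiotics given "over a 10- to 21-day treatment period", so a recurrence can end Part A follow-up before Week 8.

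**The concern.** Take a participant randomised three weeks before the cut. If still in follow-up, this person has partial data and is left out. If already withdrawn, lost, or moved to Part B after a recurrence, this person has a final outcome, almost always failure, and could be counted as one of those who left early.

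On that reading the open 8-week window contributes essentially only failures. Membership of the interim cohort then depends on outcome, and the participants left for the second stage are depleted of failures. That is the opposite of the independence section 8.8 asks for. Because the interim can stop the trial for efficacy, a cohort selected on outcome could in principle distort that decision. The differing examples of early exit (recurrence named in 3.1 but not in the synopsis or 8.10) leave unclear how many such participants there would be.

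**Working it through.** **1. The plan's own figure.** 217/324 = 0.670, so the stated 67% holds.

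**2. Inputs.** From the protocol: 324 participants, 2:1 allocation, 8-week endpoint, 217 at the interim, boundary 0.007. Illustrative rates come from the earlier trial in section 1.5.2, whose 74.5% and 61.5% are read as recurrence-free (the text prints them as recurrence rates but calls CP101 lower). That gives recurrence of 25.5% and 38.5%. Assumed, because not in the document: accrual of 2, 5 or 10 per week; 8% dropout, scored as failure and spread evenly over time; recurrences mostly early; 0.007 read as one-sided, with a final one-sided threshold of 0.0227 so that the total is 0.025.

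**3. Reference cut (first 217 randomised).** Failure rate = 1 − (1 − recurrence) × (1 − dropout).

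- CP101: 1 − 0.745 × 0.92 = 0.315
- Placebo: 1 − 0.615 × 0.92 = 0.434
- Difference: 12.0 points

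**4. Adverse cut by hand, 5 per week, every failure counted at once.** The open window holds 8 × 5 = 40 people, about 10 of whom have already failed by the cut. The other 207 have a full window: 138 on CP101 and 69 on placebo. Expected eventual failures among the 40 are 26.7 × 0.315 = 8.4 on CP101 and 13.3 × 0.434 = 5.8 on placebo, so the 10 split about 5.9 to 4.1.

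- CP101: (138 × 0.315 + 5.9)/(138 + 5.9) = 0.343
- Placebo: (69 × 0.434 + 4.1)/(69 + 4.1) = 0.466
- Difference: 12.3 points

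The extra failures enter in proportion to each arm's own failure rate. Both rates rise and the difference hardly moves.

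**5. Simulation of the same comparison** (12,000 trials per scenario, pooled z-test). Rates are CP101/placebo.

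| Cut | Open-window participants (counted) | Interim rates, % | Difference, points | Later cohort, % | Overall power, % | Effective information |
|---|---|---|---|---|---|---|
| First 217 randomised | none | 31.4/43.4 | 12.0 | as interim | 55.8 | 0.67 |
| Adverse, 2 per week | 16 (4) | 32.5/44.7 | 12.2 | 29.3/40.9 | 55.8 | 0.68 |
| Adverse, 5 per week | 40 (10) | 34.2/46.5 | 12.4 | 26.1/37.0 | 55.7 | 0.71 |
| Adverse, 10 per week | 80 (20) | 36.9/49.6 | 12.7 | 20.7/30.1 | 55.4 | 0.74 |

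The correlation between the two cohorts' treatment differences is 0.00 to 0.04.

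**6. Milder versions.** If a recurrence counts only on entry to Part B, after 10 to 21 days of antibiotics, and 50 to 100% of recurrences take that route, rates rise by 0.5–0.9, 1.2–2.1 and 2.3–4.1 points at the three accrual rates. If only dropouts enter early, the rise is under 1 point (at most 32.3/44.1%).

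**7. Type I error** (60,000 trials per scenario). With equal recurrence timing in both arms, overall one-sided error on the adverse cut is 2.49, 2.51 and 2.46%, against 2.51, 2.60 and 2.58% for the reference cut. Under an extreme null in which CP101 only delays recurrence (uniform timing on CP101, early on placebo), the paired increase is 0.02, 0.04 and 0.13 points; a repeat gave about 0.05 to 0.08. Only these paired differences are used, because the absolute levels for the reference cut vary between scenarios by more than the simulation error.

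**The case for a change.** The strongest case for a change is that the protocol states the cohort rule itself, gives its purpose, and words it so that the purpose can be missed. Section 8.10 passes only the definitions of success and futility to the SAP. Two statisticians following the text could analyse sets that differ by roughly 4 to 20 participants, which could tip a result lying near 0.007. The adverse reading also makes recurrence appear to fall after the interim, which could be mistaken for drift. One sentence would settle it.

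The textual gap stands, and so does the possibility of a different decision near the boundary. The rest carries less weight.

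- The readings are not on an equal footing. The synopsis, 3.1 and 8.10 ask for 8-week data, and 8.8 excludes partial data so that the cohorts stay independent. A reading that defeats this purpose is the weaker one. Counting those who left early has a plain ITT meaning: dropouts are not removed from the 217.
- The lists of exit reasons are examples, so their differences are not a contradiction.
- Near the boundary either cut gives a valid test, provided it is fixed before the interim data are unblinded. With timing assumptions that put 75% of failures in the first 4 weeks, and no separate dropout, the adverse cut raises the chance of crossing early at the earlier trial's rates by at most 2.3 points (32.5% to 34.8%, at 10 per week). Overall power is 66.0% against 66.3%. That is what a cut carrying slightly more information should do.
- The interim cohort definition is ordinary SAP or interim-charter content, and section 8.2 gives the SAP precedence on analysis detail. Part of 8.8 and all of 8.9 are not legible and may already hold the rule.

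**Conclusion.** No change to the plan follows. This is a gap in wording that analysts would fill sensibly: the aim stated in 8.8 leads to the first 217 or so randomised, analysed once each has reached Week 8 or left early. The less natural reading would raise both arms' interim rates by about 1 to 6 points and lower those of the later cohort, so interim rates by arm would need care in description. It would not materially affect the treatment difference, overall power or type I error, and the final ITT analysis of all 324 is the same on either cut. No claim of a biased efficacy decision is supported.

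The sizes rest on assumed accrual, dropout, recurrence timing and sidedness of the 0.007 boundary. The largest shifts need the fastest accrual and every recurrence counted the day it occurs; a 14-day adjudication lag brings the top figures down from 36.9/49.6% to 35.3/47.7%. The SAP was not available and may already define the cohort.

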# 8.9 Handling of Missing Data

0111,000		
		1.1.1 1.1.1
~~~		
5	24	
2		
3. <del>.</del>		

# 8.10 Determination of Sample Size

The approximate sample size is 324 with an IA planned when 8-week data are available for approximately 217 participants from the ITT population (67% information fraction), including those that discontinued earlier than 8 weeks (e.g., due to lost-to-follow-up, withdrawal of consent). This IA is intended to evaluate whether the data are sufficient to declare "success" for efficacy early based on primary efficacy endpoint, but not for evaluating "futility." Further information on the definitions of success and futility will be included in the SAP.

# 8.11 Reporting Deviations

Any deviation(s) from the original statistical plan will be described and justified in protocol and/or SAP and in the final report, as appropriate.

# 9 TRIAL MANAGEMENT AND DATA COLLECTION

#### 9.1 Confidentiality Regarding Trial Participants

Each participant will be assigned a unique and anonymized identifier in the IRT. Any participant records or datasets that are transferred to the Sponsor will contain the identifier only; participant names or any information which would make the participant identifiable will not be transferred.

The participant must be informed that his/her personal trial-related data will be used by the Sponsor in accordance with local data protection law. The level of disclosure must also be explained to the participant who will be required to give consent for their data to be used as described in the ICF.

The participant must be informed that his/her medical records may be examined by quality assurance auditors or other authorized personnel appointed by the Sponsor, by appropriate IRB/IEC members, and by inspectors from regulatory authorities.

The confidentiality of records that could identify participants must be protected, respecting the privacy and confidentiality rules in accordance with the applicable regulatory requirement(s).

#### 9.2 Source Documents

An Investigator is required to prepare and maintain adequate and accurate case histories or source documents designed to record all observations and other data pertinent to the investigation for each individual treated or entered as a control in the investigation. Source documents provide evidence for the existence of the participant and substantiate the integrity of the data collected. Source documents are filed at the Investigator's site and must be available for inspection or review throughout the trial by the Sponsor and its designees.

The Investigator may need to request previous medical records or transfer records, depending on the trial.

The Investigator must maintain accurate documentation (source data) that supports the information entered in the CRF.

#### 9.3 Case Report Forms

#### 9.4 Records Retention

# 9.5 Data Management

# 9.5.1 Data Management Responsibilities

	_	

# 9.5.2 Data Errors

Errors, omissions, or requests for clarification at the trial site will be queried; queries will be entered into the EDC system for resolution by trial sites.

# 9.5.3 Data Collection and Retrieval

# 10 TRIAL MONITORING, AUDITING, AND INSPECTING

# 10.1 Risk-Based Quality Management

The Sponsor will implement a risk-based quality management system as described in ICH E6 (R2) with methods to assure and control the quality of the trial throughout all stages of the trial process that will be proportionate to the risks inherent in the trial and the importance of the information collected. The Sponsor will identify Critical Data and Critical Processes and the respective risks associated, which will be the focus of Sponsor oversight, monitoring, and reporting activities during the conduct of this trial.

